3.2 Registration – Exclusion Criteria

3.21 Prior treatment with Pemigatinib.

3.22 Prior treatment with a selective FGFR inhibitor  $\leq$  180 days (6 months) prior to registration.

3.23 Known hypersensitivity or severe reaction to an FGFR inhibitor, or to the excipients of Pemigatinib (i.e. microcrystalline cellulose, sodium starch glycolate, and magnesium stearate).

3.24 Current evidence of clinically significant corneal or retinal disorder confirmed by ophthalmologic examination.

3.25 Treatment with other investigational study drug for any indication for any reason, or receipt of anticancer medications  $\leq$  14 days prior to registration.

3.26 Major surgery  $\leq$  28 days prior to registration.

3.27 External beam radiation therapy  $\leq$  28 days prior to registration, or palliative radiation for non-CNS disease  $\leq$  14 days prior to registration.

3.28 Brain metastases, central nervous system (CNS) metastases, leptomeningeal disease, or spinal cord compression

NOTE: Patients who are asymptomatic or previously treated and stable, without evidence of progression for  $\geq$  28 days prior to registration are eligible

NOTE: Patients taking concomitant corticosteroids and/or anticonvulsants are allowed if patient is on a stable or decreasing dose of such treatment for  $\geq$  28 days prior to registration.

3.29 History or presence of significant cardiovascular disease or condition including:

- Uncontrolled angina pectoris (Canadian Cardiovascular Society Grade II-IV despite medical therapy).
- Congestive heart failure (New York Heart Association Class III or IV).
- Uncontrolled arrhythmia requiring therapy. Note: Patients with a pacemaker and well-controlled rhythm for  $\geq$  28 days prior to registration are not excluded.
- Any of the following occurring  $\leq$  6 months prior to registration: Myocardial infarction, angioplasty, cardiac stenting, coronary/peripheral artery bypass graft, cerebrovascular accident or transient ischemic attack.

3.29a Failure to adequately recover (i.e. to  $\leq$  Grade 1(according to CTCAE v.5) or to pre-treatment baseline) from adverse events (AEs) deemed by the investigator as clinically significant and attributed to prior therapy.  
Exception: alopecia.

3.29b Current use of prohibited medication as described in Section 9.11.

3.29c Use of any potent CYP3A4 inhibitors or inducers or moderate CYP3A4 inducers (see Appendix II)  $\leq$ 14 days or 5 half-lives (whichever is shorter) prior to registration. Note: Topical ketoconazole will be allowed.

3.29d History of hypovitaminosis D requiring supraphysiologic doses to replenish the deficiency. Note: Patients receiving vitamin D food supplements are allowed.

3.29e History and/or current evidence of ectopic mineralization/calcification, including but not limited to soft tissue, kidneys, intestine, myocardia, or lung; with the exception of calcified lymph nodes and asymptomatic arterial or cartilage/tendon calcification.

3.29f Unable or unwilling to swallow Pemigatinib and keep a medication diary, or significant gastrointestinal disorder(s) that could interfere with absorption, metabolism or excretion of Pemigatinib per the discretion of the investigator.

3.29g Any of the following because this study involves an investigational agent whose genotoxic, mutagenic and teratogenic effects on the developing fetus and newborn are unknown:

- Pregnant women.
- Nursing women.
- Women of childbearing potential or men able to father children who have a female partner of childbearing potential, who are unwilling to employ acceptable contraception as outlined in Appendix I.

3.29h Known history of human immunodeficiency (HIV) infection or positivity on immunoassay confirmed per local standards

Note: HIV test is not required for screening, but patients with a known history of HIV infection will be excluded.

3.29i Evidence of active hepatitis B (HBV) or hepatitis C (HCV) infection

3.29j Other known active malignancy  $\leq$  5 years prior to registration.

**EXCEPTIONS:** Non-melanotic skin cancer or carcinoma in situ of the cervix, provided there is no known active disease and no additional therapy for the condition is ongoing or required during the trial period

**NOTE:** Anti-estrogen/androgen therapy or bisphosphonates allowed.

3.29k Co-morbid systemic illness, other severe concurrent disease, or psychiatric illness/social situation which, in the judgment of the investigator, would make the patient inappropriate for entry into this study, limit compliance with study requirements, or interfere significantly with the proper assessment of safety and

toxicity of the prescribed regimen.

## 4.0 Test Schedule

### 4.1 Schedule of Assessments

Tests and Procedures	Screening	Active Monitoring					
		Cycle 1			Cycles 2 +	End of Treatment	Safety 
	Days -28 to -1	Day 1 	Day 8 ±3 days 	Day 15 ±3 days 	Day 1 ±3 days 	Last day of treatment +14 days 	EOT +30-35 days
COLOMATE Companion Trial Recommendation Form(optional) 	X						
Demography and medical history	X						
Hepatitis B and C screening	X						
Vital Signs, ECOG performance status 	X	X	X	X	X	X	X
Physical exam, weight, height	X	X	X	X	X	X	X
Review AEs	X	X	X	X	X	X	X
Review prohibited meds 	X	X	X	X	X	X	X
Review patient medication diary			X	X	X	X	
Eye examination R	X				X  (every 3 cycles starting with c3d1)	X	

Tests and Procedures	Screening	Active Monitoring					
		Cycle 1			Cycles 2 +	End of Treatment	Safety 
	Days -28 to -1	Day 1 	Day 8 ±3 days 	Day 15 ±3 days 	Day 1 ±3 days 	Last day of treatment +14 days 	EOT +30-35 days
CT or MRI 	X				X  (Restaging at end of cycles 3, 6, 9 etc.)	X 	
12-lead ECG 	X	X		X	X	X	X
Hematology and Serum Chemistries	X	X	X	X	X	X	X
Tumor Blood Biomarkers (CEA) 	X 	X			X		
Coagulation panel	X				X  (day 1 of c4, 7, 10 etc.)	X	
Parathyroid hormone (PTH) R	X	X			X	X	
Lipid panel R		X				X	
Mandatory Patient Questionnaire Booklet (Appendix V) 		X			X	X	
Urinalysis	X				X  (day 1 of c4, 7, 10 etc.)		

Tests and Procedures	Screening	Active Monitoring					
		Cycle 1			Cycles 2 +	End of Treatment	Safety 
	Days -28 to -1	Day 1 	Day 8 ±3 days 	Day 15 ±3 days 	Day 1 ±3 days 	Last day of treatment +14 days 	EOT +30-35 days
Pregnancy test 	X 	X			X	X	
Blood sample-cfDNA Guardant360 (optional) 13,R						X	
Mandatory archival tissue 8,R	X						
Mandatory blood sample plasma 9,R		X			X  (c2d1; then on d1 following restaging scans (c4, 7, 10, etc.))	X	
Mandatory blood sample- Whole blood R		X 					

**Notes:**

R Research funded (see Section 19).

1. If the subject is participating through the COLOMATE platform: The COLOMATE Companion Trial Recommendation Form must indicate that the patient has met molecular eligibility to screen. The patient must be registered to the companion study ≤30 days from date of COLOMATE Companion Trial Recommendation Form completion. If the COLOMATE Companion Trial Recommendation Form recommends a different companion study, patient may still enroll after approval by the study PI or designee. Form must be uploaded to supporting documentation folder in RAVE.

2. Vital Signs: Including heart rate, blood pressure and temperature (oral or tympanic) and ideally performed with subject in a recumbent or semirecumbent position after 5 minutes of rest.
3. Prohibited Medications: List of prohibited medications in section 9.11 should be reviewed at study entry and during treatment.
4. Comprehensive Eye Examination: To be performed by a qualified ophthalmologist at screening, once every 3 cycles starting with Cycle 3, Day 1 ( $\pm 14$  days); at EOT, and as clinically indicated. The eye examination should include a visual acuity test, slit-lamp examination, OCT, and funduscopy with digital imaging. Additional assessments should be performed if clinically relevant retinal findings are observed on ophthalmologic exams and in participants with reported visual AEs or change in visual acuity, if the events or changes are suspected to be of retinal origin. Every effort should be made to ensure that all subsequent examinations are performed by the same ophthalmologist.
5. Computed Tomography (CT) / Magnetic Resonance Imaging (MRI): Baseline evaluation of disease status by CT or MRI completed  $\leq 28$  days prior to registration. Baseline and subsequent scans to include imaging of the primary site of disease plus any additional sites of known or suspected disease. Re-scanning to occur every 9 weeks (minus 1-6 days) after initiating protocol treatment on Cycle 1, Day 1. (The minus 1-6 day scan window is intended for flexibility in scheduling re-scans during Week 3 of every 3rd cycle – i.e. re-scanning intended between Days 15-21 of Cycles 3, 6, 9, etc.)  
Same-day scanning on Day 1 of Cycles 4, 7, 10, etc. is discouraged but allowed, provided scan results receive appropriate RECIST review prior to initiating/continuing Pemigatinib in the new cycle of study treatment (e.g. first re-scan is discouraged, but permitted on Cycle 4, Day 1, provided RECIST review occurs prior to dispensing Pemigatinib for Cycle 4).  
CT/MRI required at EOT only if it has been  $>28$  days since the previous CT/MRI.
6. Electrocardiogram (ECG): Single trace 12-lead ECGs on site equipment ideally performed with subject in a recumbent or semirecumbent position after 5 minutes of rest. ECGs will be interpreted locally by the site and used for subject management. Management decisions (e.g. include or exclude a subject or withdraw a subject from the study) based on an ECG finding such as "Abnormal, Clinically Significant" is the responsibility of the investigator, in consultation with the sponsor-investigator, as appropriate. Clinically notable abnormalities considered clinically significant by the investigator are to be reported as AEs.
7. Pregnancy Test: For all women of childbearing potential (WOCBP) – as defined in Appendix I – serum pregnancy test required during screening; and serum or urine pregnancy test to be conducted on Day 1 of Cycle 1 (before first dose of Pemigatinib), on Day 1 of every cycle, at the EOT visit, and additionally as medically indicated. If a urine pregnancy test is positive, the results should be confirmed with a serum pregnancy test: If the serum pregnancy test is negative after a urine test was positive, the investigator will assess the potential benefit/risk to the subject and determine whether it is in the subject's best interest to resume study drug and continue participation in the study.

8. Archival Tissue: Receipt of archival tumor tissue is not required for study registration and initiation of therapy. However, it is mandatory to receive the required tissue within 90 days from randomization. See section 17.0.
9. Mandatory Blood Sample-Plasma: Mandatory collection on Day 1, cycle 1; day 1, cycle 2; and on day 1 of each cycle which is immediately following radiographic assessment for re-staging ( day 1 of cycles 4,7,10, etc.) and at EOT (see Section 14). Kits required for collection. Patient must be registered prior to collection.
10. Administrative Scheduling Window: After Cycle 1, Day 1, allowance of  $\pm 3$  days for subsequent study visits is permitted for scheduling considerations other than adverse event management (e.g. holidays, weekends, inclement weather).
11. End-of -Treatment (EOT): Reasonable effort should be made to complete End-of-Treatment (EOT) procedures on the day it is decided a patient will no longer receive Pemigatinib. These procedures must be completed subsequent to and not later than 14 days after investigator decision to permanently discontinue Pemigatinib and prior to any subsequent anti-cancer therapy. CT/MRI required at EOT only if it has been  $>28$  days since the previous CT/MRI.
12. Safety Follow-Up: One-month follow-up (1M F/U) visit to be performed 30 to 35 days after the EOT visit. (In the event EOT visit not performed, then the safety follow-up visit is to be performed 30-35 days after the last dose of Pemigatinib.) Any adverse event in the Safety Follow-up will be recorded on the adverse event assessment form in the last cycle of treatment. The Safety Follow-up is recommended by the study protocol, but no data collection is required other than adverse event assessment.
13. Patients have the option to complete cfDNA testing at study completion and will be allowed to re-register with protocol ACCRU-GI-1611. Site will access results by creating an account at [REDACTED]. Sites will be notified by Guardant Health via email when results are available in the portal. See section 13.8. See detailed instructions on the ACCRU website under Manuals and Forms. Kits are required for this collection.
14. If screening tests occur  $\leq 3$  days prior to C1 D1, they do not have to be repeated prior to dosing.
15. Coagulation Panel: to be done at screening, restaging (day 1 of cycles 4, 7, 10 etc.) and end of treatment.
16. Urinalysis: to be done at screening and restaging (day 1 of cycles 4, 7, 10, etc.).
17. Mandatory blood sample-Whole blood: May occur prior to treatment on cycle 1 day 1. Refer to section 14.0
18. Tumor Blood Biomarkers (CEA): to be done  $\leq 7$  days prior to registration, and day 1 of every cycle thereafter.

19. Patient questionnaire will be completed at baseline, day 1 of each cycle, and end of treatment (within 30 days of last dose as noted in appendix V). Patient questionnaire booklets must be used; copies are not acceptable for this submission. The booklet order form is located on the ACCRU website under Manuals and Forms.

## 4.2 Local Laboratory Tests: Required Analytes

Serum Chemistries	Hematology	Urinalysis with Microscopic Examination	Hepatitis Screening	Coagulation
Albumin Alkaline phosphatase ALT AST Bicarbonate Blood urea nitrogen Calcium Chloride Creatinine Glucose Lactate dehydrogenase Phosphate Potassium Sodium Total bilirubin Total protein Uric acid Vitamin D (25-hydroxyvitamin D and 1,25-dihydroxyvitamin D)	
Complete blood count, including:
 
 
• Hemoglobin
 
• Hematocrit
 
• Platelet count
 
• Red blood cell count
 
• White Blood cell count
 
 
Differential count, including:
 
 
• Basophils
 
• Eosinophils
 
• Lymphocytes
 
• Monocytes
 
• Neutrophils
 
 
Absolute values must be provided for: WBC differential laboratory results: Lymphocytes Neutrophils
	
Color and appearance pH and specific gravity Bilirubin Glucose Ketones Leukocytes Nitrite Occult blood Protein Urobilinogen
	
Hepatitis B surface antigen Hepatitis B surface antigen antibody Hepatitis B core antibody HCV antibody
 
NOTE: If any of the above are positive, then HBV-DNA, HCV-RNA to assess risk of reactivation.
	PT PTT INR
		Lipid Panel	Other	Pregnancy Testing
		Total cholesterol Triglycerides LDL HDL	Endocrine: Parathyroid hormone	Required only for female subjects of childbearing potential. Serum pregnancy test at screening; and serum or urine pregnancy test on Day 1 of Cycle 1 (before first dose of Pemigatinib), on Day 1 of every cycle, and at EOT.

## 5.0 Grouping Factors

Type of FGFR alteration:

- Mutations Vs.
- Translocations/Fusion Vs.
- Amplifications

## 6.0 Registration Procedures

### 6.1 Registration Procedures

6.11 To register a patient, fax ( [REDACTED] ) a completed eligibility checklist to the Academic and Community Cancer Research United (ACCRU) Registration Office between 8 a.m. and 4:30 p.m. central time Monday through Friday.

**Only required if patient is participating in ACCRU-GI-1611.** NOTE: ACCRU-GI-1611 (COLOMATE) treating physician will provide COLOMATE Companion Trial Recommendation Form which will include the Patient ID that must be used for this study.

#### 6.12 Mandatory

A mandatory correlative research component is part of this study. The patient will be automatically registered onto this component (see Sections 3.0, 14.0 and 17.0).

#### Optional

An optional correlative research component is part of this study. There will be an option to select if the patient is to be registered onto this component (see Section 14.0).

- Patient has/has not given permission to give his/her blood sample for research testing.

6.13 Documentation of IRB approval must be on file in the Registration Office before an investigator may register any patients. Approvals should be uploaded using the online ACCRU Regulatory Management System (ARMS).

In addition to submitting initial IRB approval documents, ongoing IRB approval documentation must be on file (no less than annually) with ACCRU. Approvals should be uploaded using the online ACCRU Regulatory Management System (ARMS). If the necessary documentation is not submitted in advance of attempting patient registration, the randomization will not be accepted and the patient may not be enrolled in the protocol until the situation is resolved.

Submission of annual IRB approvals is required until the study has been closed through your IRB.

6.14 Prior to accepting the registration/randomization, the registration/randomization application will verify the following:

- IRB approval at the registering institution
- Patient eligibility
- Existence of a signed consent form
- Existence of a signed authorization for use and disclosure of protected health information

6.15 At the time of registration, the following will be recorded:

- Patient has/not given permission to store and use his/her blood sample(s) for future research to learn about, prevent, or treat cancer.
- Patient has/not given permission to store and use his/her blood sample(s) for future research to learn, prevent, or treat other health problems (for example: diabetes, Alzheimer's disease, or heart disease).
- Patient has/not given permission to store and use his/her tissue sample(s) for future research to learn about, prevent, or treat cancer.
- Patient has/not given permission to store and use his/her tissue sample(s) for future research to learn, prevent, or treat other health problems (for example: diabetes, Alzheimer's disease, or heart disease).
- Patient has/not given permission for ACCRU to give his/her sample(s) to outside researchers.

6.16 Treatment cannot begin prior to registration and must begin  $\leq$ 10 days after registration.

6.17 Pretreatment tests/procedures (see Section 4.0) must be completed within the guidelines specified on the test schedule.

6.18 All required baseline symptoms (see Section 10.5) must be documented and graded.

6.19a Treatment on this protocol must commence at an ACCRU institution under the supervision of a medical oncologist.

6.19b Blood draw kit is available on site.

Note: Guardant 360 kit does not need to be on site at the time of registration.

6.19c Patient questionnaire booklet is available on site; copies are not acceptable for this submission.

## 7.0 Protocol Treatment

### 7.1 Treatment Schedule

Agent	Dose	Route	Schedule
Pemigatinib	13.5 mg (dose level 0)	Oral	Once daily (QD), on Days 1-21 of cycle 1
Pemigatinib	18 mg*	Oral	Once daily (QD), on Days 1-21 of cycles 2-35*

During each 21-day dosing cycle, Pemigatinib is scheduled to be administered on days 1-21 of a 21 day cycle

Each dose of Pemigatinib should be taken by mouth with a glass of water immediately upon rising or after a 2-hour fast. After dosing, the patient should refrain from eating for 1 hour.

If the subject vomits after taking study drug, the subject should not take another dose that day. If a dose of Pemigatinib is missed by more than 4 hours, that dose should be skipped and the next scheduled dose should be administered at the usual time.

**\*All of the following criteria must be met in order to increase dose level beginning at cycle 2**

- Participant does not reach the target serum phosphate level of > 5.5 mg/dL at any time during Cycle 1.
- Patient is compliant with taking study drug.
- Patient does not experience an ongoing Grade 2 or higher treatment-related AEs during cycle 1.
- If dose level escalated, please remember to report as modified treatment in Rave.

7.2 If all criteria for dose increase are not met patient will remain at dose level 0. Dose may be increased at a future cycle if patient meets criteria. Note: If dose escalated, please remember to report as modified treatment in Rave.

7.3 Patients can be instructed in Pemigatinib administration techniques and granted treatment independence with nursing staff approval.

7.4 For this protocol, the patient must return to the consenting ACCRU institution for evaluation during treatment and during observation (Active Monitoring Phase) according to the table in Section 4.0.

7.5 Patients will be required to keep a medication diary for Pemigatinib using the diary in appendix III. Sites will be required to upload medication diary to RAVE at the end of each cycle.

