The increase in serum phosphorus observed after treatment with pemigatinib was exposure-dependent and followed a sigmoid relationship. A population Emax model of pemigatinib AUC and maximal serum phosphate change from baseline was developed. For those participants treated with pemigatinib 13.5 mg who did not develop hyperphosphatemia, AUC for pemigatinib 18 mg was estimated using a linear exposure relationship. Maximal serum phosphate change from baseline for each individual was then estimated using a population model. The maximal serum phosphate after treatment with pemigatinib 18 mg was calculated by adding the baseline of serum phosphate. The simulation suggested that the serum phosphate would increase above 5.5 mg/dL after treatment with pemigatinib 18 mg for the participants treated with pemigatinib 13.5 mg who did not develop hyperphosphatemia.

Figure 2: Comparison of Steady State Exposures for Pemigatinib 13.5 mg QD Between Subjects With Nonhyperphosphatemia and Hyperphosphatemia

AUCss = area under the curve at steady state; Css, min = minimum blood plasma concentration at steady state; HP = hyperphosphatemia.

Any participant who does not reach the target serum phosphate level of  $> 5.5$  mg/dL at any time during Cycle 1, and who is compliant with taking study drug and does not experience an ongoing Grade 2 or higher treatment-related AEs, will increase the daily dose to 18 mg starting at Cycle 2 Day 1. Participants who are titrated up to 18 mg QD will begin the next cycle at the new dose level and must agree to all Cycle 1 assessments (PK and safety assessments [hematology and blood chemistry]). Up-titration may occur no earlier than on Day 1 of Cycle 2, so that participants are observed for phosphate level and AEs at least for 1 cycle.

For participants who are up-titrated from 13.5 mg to 18 mg, a maximum of 2 dose level reductions is also recommended: 18 mg can be decreased to 13.5 mg, and if additional dose reduction is required, participants can decrease to 9 mg. Dose reductions below 9 mg are not allowed."

[figure not shown]
A CYP3A4-mediated drug-drug interaction study (INCB 54828-104) indicated there is evidence of a clinically significant effect on pemigatinib exposure when co-administered with a potent CYP3A4 inhibitor, itraconazole (increased pemigatinib AUC by 88%) or

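### Read literally, the 18 mg phosphate criterion counts only Cycle 1 values, so a patient who first exceeds 5.5 mg/dL at Cycle 2 Day 1 or later still meets it

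*Combined protocol and SAP*

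**What the plan says.** Section 1.5 gives the purpose. Some patients on 13.5 mg do not become hyperphosphatemic and probably have lower drug exposure, and up-titration is meant to raise exposure in them. The section describes hyperphosphatemia as any phosphate above 5.5 mg/dL after baseline. Neither statement is limited to a cycle.

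The operative rule is limited to one.

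- Section 7.1 lists 18 mg for cycles 2 to 35, subject to asterisked criteria: "All of the following criteria must be met in order to increase dose level beginning at cycle 2".
- The phosphate criterion is: "Participant does not reach the target serum phosphate level of > 5.5 mg/dL at any time during Cycle 1". Section 1.5 uses the same Cycle 1 window and says that a qualifying participant "will increase the daily dose to 18 mg starting at Cycle 2 Day 1".
- Section 7.2 keeps other patients at 13.5 mg and adds: "Dose may be increased at a future cycle if patient meets criteria". It does not restate or move the window.
- The adverse-event criterion in 7.1 reads: "Patient does not experience an ongoing Grade 2 or higher treatment-related AEs during cycle 1". The version in 1.5 has no cycle limit: "does not experience an ongoing Grade 2 or higher treatment-related AEs".

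The test schedule in 4.1 places serum chemistries, which include phosphate, on Days 1, 8 and 15 of Cycle 1 and then on Day 1 of each later cycle.

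**The concern.** The purpose depends on how a patient responds to 13.5 mg. The criterion depends on a calendar window. The two come apart when phosphate first exceeds 5.5 mg/dL after Cycle 1 while the patient is still on 13.5 mg. Such a patient has reached the target yet still satisfies the phosphate bullet as written.

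What is at stake is an individual patient's dose. The argument for 18 mg in 1.5 rests on a simulation in participants who did not develop hyperphosphatemia on 13.5 mg. Escalating someone who has developed it falls outside that argument. Two sites reading the rule differently would also give similar patients different doses.

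**Working it through.** The point concerns wording, so the main check is to set the sections side by side. There is no plan figure to reproduce.

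**Case 1: the Cycle 2 Day 1 draw (illustrative values).** A compliant patient with no disqualifying adverse event has phosphate 4.9 mg/dL on Day 8, 5.4 on Day 15 and 5.9 at Cycle 2 Day 1.

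- Criterion in 1.5 and 7.1: no Cycle 1 value exceeds 5.5, so it is met.
- Section 1.5: the increase starts at that visit.
- Purpose in 1.5: the patient has become hyperphosphatemic on 13.5 mg, so the increase is not intended.
- Section 8.2: above 5.5 and up to 7 mg/dL, start a low-phosphate diet, with no action on the drug. Nothing there bars an increase.

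**Case 2: the delayed increase (illustrative values).** A patient stays at or below 5.5 mg/dL in Cycle 1 but is not compliant, so remains on 13.5 mg. In Cycle 2 the patient is compliant and reaches 6.5 mg/dL.

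- Section 7.2: an increase may be considered at Cycle 3 Day 1 if the criteria are met.
- Phosphate bullet in 7.1: it refers only to Cycle 1, so it is still met.
- Section 8.3: prior discussion is required for re-escalation; a first increase is not mentioned.

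**Adverse-event criterion.** The mismatch with 7.2 runs the other way. A patient whose Grade 2 event was ongoing in Cycle 1 and resolved in Cycle 2 fails the 7.1 bullet for good if it is read literally, although 7.2 appears to allow a later increase. The 1.5 version does not have this effect.

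**Size of the dose step.** 18 − 13.5 = 4.5 mg, and 4.5/13.5 = 0.333, so +33%. Section 1.5 states that "AUC for pemigatinib 18 mg was estimated using a linear exposure relationship". On that basis AUC also rises by about 33%.

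**Number of patients affected.** Table 13 shows hyperphosphatemia in 14 of 16 patients on 13.5 mg continuous dosing (14/16 = 87.5%). It does not say when each patient first exceeded 5.5 mg/dL, so the share crossing after Cycle 1 cannot be calculated.

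**The case against.** The strongest reply is that a sensible site would not follow the literal reading.

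- Section 7.2 is permissive and in the present tense, so it can be taken as a fresh assessment in the current cycle. A frozen Cycle 1 window would leave 7.2 serving little beyond Cycle 1 non-compliance.
- Section 1.5 puts the earliest increase at Cycle 2 Day 1 so that phosphate and adverse events are watched for at least one cycle. A site could count the Cycle 2 Day 1 value as completing that observation.
- The broad description of hyperphosphatemia in 1.5 reports incidence already seen; it is not itself an escalation test.
- Late first crossings may be uncommon. With the mean half-life of 15 hours in 15.15, five half-lives take 75 hours, about 3 days. At the upper end in 1.6 (31.4 hours) they take 157 hours, about 6.5 days. Exposure is therefore near steady state by Day 8.

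Much of this stands and limits the point. It does not remove it: none of these passages rewrites the criterion, phosphate may lag behind exposure, and Case 2 does not depend on early kinetics.

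Three stronger readings are tempting, and the documents do not support them.

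- A reader might infer that the plan compels overdosing. The mandatory wording appears only in 1.5 and only for the Cycle 2 Day 1 start. Section 7 states necessary conditions and says that the dose may be increased.
- A reader might count the study days after the Day 15 draw as a measure of the gap, or argue that an early Cycle 2 Day 1 visit within its 3-day window would count as Cycle 1. Both need a fixed cycle boundary. The plan does not say whether the boundary moves with the visit, and 8.3 lets a cycle run to 35 days after a hold. Days without a scheduled value are in any case not misdosed patients.
- A reader might infer a threat to the efficacy conclusion. The decision rule in 16.21 and its error rates do not depend on this wording.

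**Conclusion.** The point holds as a minor defect of wording. Read literally, the phosphate criterion can be met by a patient already above 5.5 mg/dL on 13.5 mg, contrary to the purpose in 1.5. The consequence for such a patient is a dose one third higher. This rests on the literal reading, on the compliance and adverse-event criteria also being met, and, for the exposure figure, on dose-proportional AUC.

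Harm is bounded:

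- Section 1.4 reports no monotherapy dose-limiting toxicity and no maximum tolerated dose reached. Doses up to 20 mg were given, including to 6 patients on continuous dosing.
- Section 1.5 requires the Cycle 1 safety assessments to be repeated after up-titration.
- Above 7 mg/dL, 8.2 starts phosphate binders and holds the drug if the level persists or recurs, so the practical gap is mainly between 5.5 and 7 mg/dL.
- Hyperphosphatemia is graded at each evaluation under 10.52. Depending on its grade and attribution, it might itself block the increase under the adverse-event clause in 1.5.

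Frequency is unknown. This is a cheap improvement, not a condition for the trial to proceed.

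**What to change.** Use the same text in 1.5, 7.1 and 7.2:

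- Phosphate: *no serum phosphate > 5.5 mg/dL at any time on 13.5 mg, up to and including the scheduled Day 1 result of the cycle in which the increase would start, reviewed before the increased dose is given.*
- Adverse events: *no ongoing Grade 2 or higher treatment-related AE at the time of the increase.*
- Compliance: leave unchanged.

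This ties the test to response on 13.5 mg, makes 7.2 workable for both criteria, and removes any dependence on where a cycle is taken to end.

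The cost is a wording amendment in three places. No samples are added, because chemistries are already scheduled on Day 1 of every cycle. There are two downsides. The first 18 mg dose may have to wait for the Day 1 result, with 13.5 mg continued meanwhile. A single transient value just above 5.5 mg/dL also bars any later increase; the literal rule already does this for a value in Cycle 1, so the change extends that bar to later cycles.
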